4.7. Pharmacokinetic Evaluations

Not Applicable.

4.8. Safety Analyses

Unless specified otherwise, safety analyses will be conducted using the SAF analysis set, and presented based on actual treatment received.

4.8.1. Treatment Exposure and Compliance

Time on study (follow-up) in weeks and subject-years on study as defined in sections 4.2.14 and 4.2.18 will be summarised as continuous variables. Time on study drug as defined in section 4.2.15 will also be summarised.

Treatment Exposure

The number of injections of study drug per subject will be summarised as a categorical variable (1, 2, 3, 4). The total amount of study drug given and planned (see Table 6 and Table 7) across

visits (mL) will be calculated for each subject, and will be summarised by treatment group. Summary statistics for the doses received (in mL and in mg) at each visit be also presented.

The total amount of study drug and the doses received at each visit in mL and mg will also be summarised as a continuous variable.

Treatment Compliance

The planned dose will be derived based on the protocol number, protocol consent and re-consent dates, serum pregnancy test result, weight, Hb levels, and ID status as per Table 6 and Table 7 below. Table 7 will apply only for subjects who consented to protocol 2 or 3 or if the subject re-consented to protocol 2 and the injection date is on or after the protocol re-consent date. ID is defined as serum ferritin <100 ng/mL, or $100 \text{ ng/mL} \leq \text{serum ferritin} \leq 299 \text{ ng/mL}$ if transferrin saturation (TSAT) is <20%. The laboratory and vital sign values closest to the injection date and time (\leq) will be used. In case no injection was done, the value closest to the visit date will be used.

For the protocol 1, the first dose of study treatment is administered for all randomised subjects on the same day as randomisation – i.e., at Visit 2 while the subject is still hospitalised for the Index hospitalisation. The subsequent administrations of study treatment are done as part of the outpatient clinic visits at Week 6 (Visit 3), and at Weeks 12 (Visit 4) and 24 (Visit 5) only for subjects in whom ID persists and for whom $\text{Hb} \geq 8 \text{ g/dL}$ and $\leq 15 \text{ g/dL}$. The serum pregnancy test must also be negative for the respective visit for females of childbearing potential.

The dosing regimen for protocol 1.2 is similar to the one from protocol 1 except for the subjects from The Netherlands (NL). For NL subjects, the lower threshold of Hb values is set to 10 g/dL.

For the protocol 2 and 3, dosing at Week 6 (Visit 3) is based on the iron need upon screening Hb and weight values to replete iron as described in Table 7 and only be done in subjects for whom $\text{Hb} \leq 15 \text{ g/dL}$. Maintenance dosing at Weeks 12 (Visit 4) and 24 (Visit 5) is only for subjects in whom ID persists and for whom $\text{Hb} \geq 8 \text{ g/dL}^*$ and $\leq 15 \text{ g/dL}$ at those visits. The serum pregnancy test must also be negative for the respective visit for females of childbearing potential.

* Following section in italics is applicable for The Netherlands, Spain and Singapore only (**NL, ES and SG only**):

The lower threshold of Hb values is set to 10 g/dL.

Table 6 Study drug Dosing Regimen Protocol 1

Treatment Visit	Total mL FCM or Saline				
	Weight <70 kg		Weight ≥70 kg		Any Weight
	8 g/dL ≤ Hb < 10 g/dL	10 g/dL ≤ Hb ≤ 14 g/dL	8 g/dL ≤ Hb < 10 g/dL	10 g/dL ≤ Hb ≤ 14 g/dL	
Visit 2 (Week 0)	2x10 mL				1x10 mL
Visit 3 (Week 6)	1x10 mL (only if ID persists)	No dose	2x10 mL (only if ID persists)	1x10 mL (only if ID persists)	No dose
Visit 4, Visit 5 (Week 12, Week 24)	1x10 mL (only if ID persists)				

Notes: FCM=Ferric carboxymaltose; Hb=Haemoglobin; ID=Iron deficiency.

Table 7 Study drug Dosing Regimen Protocols 2, 3

Treatment Visit	Total mL FCM or Saline				
	Weight <70 kg		Weight ≥70 kg		Any Weight
	8 g/dL ⁽¹⁾ ≤ Hb <10 g/dL	10 g/dL ≤ Hb ≤14 g/dL	8 g/dL ⁽¹⁾ ≤ Hb <10 g/dL	10 g/dL ≤ Hb ≤14 g/dL	
Visit 2 (Week 0)	2x10 mL				1x10 mL
Visit 3 ⁽²⁾ (Week 6)	1x10 mL	No dose	2x10 mL	1x10 mL	No dose
Visit 4, Visit 5 (Week 12, Week 24)	1x10 mL (only if ID persists)				

1 Following section in italics is applicable for The Netherlands, Spain and Singapore only (NL, ES and SG only): *The lower threshold of Hb values for subject eligibility prior to enrolment into the study is set to 10 g/dL. Subjects enrolled in the study in NL, ES and SG only with Hb levels that are falling below the threshold of 10 g/dL during the study will need to be withdrawn from further study treatment dosing.*

2 Dosing at Week 6 (Visit 3) will be based on the iron need upon screening Hb and weight values and only be done in subjects for whom Hb at Week 6 (Visit 3) ≤15 g/dL.

Notes: FCM=Ferric carboxymaltose; Hb=Haemoglobin; ID=Iron deficiency.

The algorithm to calculate the planned dose is described in Appendix II.

The calculated planned dose and the dose administered as collected in the eCRF will be used to calculate the dosing information (dose given as planned, reduced, increased). It will be summarised for each treatment visit (Baseline, Visit 3 [Week 6], Visit 4 [Week 12], and Visit 5 [Week 24]).

The total amount of study drug given during the study will be calculated for each subject and will be compared to the amount expected to be given for each subject based on weight, Hb levels, and ID status. Treatment compliance will be calculated for each subject and summarised by treatment group and summarised as continuous and categorical variable (<80, 80-120, > 120 as categories)

- Total amount = total volume administered in mL over all visits.
- Expected amount = total volume in mL that should have been administered as described in Table 6.
- Compliance rate = (total amount/expected amount)*100.

Treatment compliance and drug concentration information will also be reported in data listings.

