Appendix II: Calculation of planned dose

Protocol Number	Planned Dose
1, 1.1, 1.2 and country NE The Netherlands, Singapore, Spain	
"Hemoglobin in g/dL" < 8: No dose "Hemoglobin in g/dL" > 15: No dose
 
Visit 2 If "Serum pregnancy test" = "Positive": No dose 8 ≤ "Hemoglobin in g/dL" ≤ 14: 2 Kits 14 < "Hemoglobin in g/dL" ≤ 15: 1 Kit
 
Visit 3 If "Serum pregnancy test" = "Positive": No dose "Weight in kg" < 70 and 8 ≤ "Hemoglobin in g/dL" < 10 and "ID persists" : 1 Kit "Weight in kg" < 70 and 10 ≤ "Hemoglobin in g/dL" ≤ 14 : No dose "Weight in kg" ≥ 70 and 8 ≤ "Hemoglobin in g/dL" < 10 and "ID persists" : 2 Kits "Weight in kg" ≥ 70 and 10 ≤ "Hemoglobin in g/dL" ≤ 14 and "ID persists" : 1 Kit "Hemoglobin in g/dL" > 14 : No dose
 
Visit 4 and Visit 5 If "Serum pregnancy test" = "Positive": No dose "ID persists" : 1 Kit

2, 3 and country NE The Netherlands, Singapore, Spain	
"Hemoglobin in g/dL" < 8: No dose "Hemoglobin in g/dL" > 15: No dose
 
Visit 2 If "Serum pregnancy test" = "Positive": No dose 8 ≤ "Hemoglobin (from screening) in g/dL" ≤ 14: 2 Kits 14 < "Hemoglobin (from screening) in g/dL" ≤ 15: 1 Kit
 
Visit 3 If "Serum pregnancy test" = "Positive": No dose "Weight in kg" < 70 and 8 ≤ "Hemoglobin (from screening) in g/dL" < 10 : 1 Kit "Weight in kg" < 70 and 10 ≤ "Hemoglobin (from screening) in g/dL" ≤ 14 : No dose "Weight in kg" ≥ 70 and 8 ≤ "Hemoglobin (from screening) in g/dL" < 10: 2 Kits "Weight in kg" ≥ 70 and 10 ≤ "Hemoglobin (from screening) in g/dL" ≤ 14 : 1 Kit "Hemoglobin in g/dL" > 14 : No dose
 
Visit 4 and Visit 5 If "Serum pregnancy test" = "Positive": No dose "ID persists" : 1 Kit

Protocol Number	Planned Dose
If country = The Netherlands, Singapore, Spain	Same calculation as described above applies depending on protocol version. However, replace lower threshold for Hemoglobin by 10 g/dL instead of 8 g/dL.

Note:

ID is defined as serum ferritin <100 ng/mL, or $100 \text{ ng/mL} \leq \text{serum ferritin} \leq 299 \text{ ng/mL}$ if transferrin saturation (TSAT) is <20%. The laboratory and vital sign values closest to the injection date and time (\leq) is used. In case no injection was done, the value closest to the visit date will be used.

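### SAP 4.8.1 takes the expected dose from the protocol 1 table only, so some protocol 2/3 subjects dosed as planned at Week 6 without iron deficiency score above 120% compliance

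*SAP*

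**What the plan says.** SAP 4.8.1 calculates a compliance rate per subject: 100 times the volume given over all visits, divided by an expected amount. The rate is summarised as a continuous variable and in three categories: below 80, 80 to 120, and above 120. The denominator is set in one bullet: "Expected amount = total volume in mL that should have been administered as described in Table 6". That table is headed "Table 6 Study drug Dosing Regimen Protocol 1", and each of its non-zero Week 6 entries depends on ID, for example "2x10 mL (only if ID persists".

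The rest of the section works by protocol version. The exposure paragraph cites both tables: "The total amount of study drug given and planned (see Table 6 and Table 7". The compliance paragraph says "Table 7 will apply only for subjects who consented to protocol 2 or 3", or to injections on or after re-consent to protocol 2. Footnote 2 of Table 7 reads "Dosing at Week 6 (Visit 3) will be based on the iron need upon screening Hb and weight values". It adds a ceiling of 15 g/dL on the Week 6 Hb but no ID condition. Appendix II turns this into a version-specific algorithm.

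For the Netherlands, Spain and Singapore, 4.8.1 states for protocols 2 and 3 that "The lower threshold of Hb values is set to 10 g/dL", and Appendix II says to "replace lower threshold for Hemoglobin by 10 g/dL instead of 8 g/dL". Table 6 itself carries no such limit.

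**The concern.** The section gives the same protocol 2/3 subject two totals: a planned volume based on the regimen that applied, and an expected volume based on a regimen that did not. They differ when the subject has no ID at Week 6 and Table 7 still assigns a dose. The volume given then exceeds the Table 6 expectation although dosing followed the plan, and the compliance table would show that subject as over-dosed.

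Appendix II has a second, separate defect. For protocols 2/3, four Visit 3 lines use the screening Hb, but the last line (no dose above 14 g/dL) does not say which Hb it uses. None of the lines says which weight. This affects the planned dose and therefore the by-visit summary of doses given as planned, reduced or increased.

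**Working it through.** The SAP states no compliance figure, so there is nothing to reproduce. The check applies its own formula to each cell.

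**Inputs** (SAP Tables 6 and 7; one kit is 10 mL). Visit 2: 20 mL, or 10 mL if Hb is above 14 up to 15 g/dL; the tables agree. Week 6: as tabulated below. Visits 4 and 5: 10 mL each if ID is present, so M = 0, 10 or 20 mL in total.

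**Assumptions.** Protocol 2/3 subject; no ID at Week 6; dosed per Table 7; same weight/Hb cell at screening and Week 6; Week 6 Hb 8 to 15 g/dL; same maintenance doses expected under both tables.

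**Formula.** Rate = 100 × (Visit 2 + Table 7 Week 6 dose + M) / (Visit 2 + 0 + M). The zero is the Table 6 Week 6 dose without ID.

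| Cell | Visit 2 (mL) | Week 6, Table 7 (mL) | M = 0 | M = 10 | M = 20 |
|---|---|---|---|---|---|
| <70 kg, Hb 8 to <10 | 20 | 10 | 30/20 = 150% | 40/30 = 133% | 50/40 = 125% |
| ≥70 kg, Hb 8 to <10 | 20 | 20 | 40/20 = 200% | 50/30 = 167% | 60/40 = 150% |
| ≥70 kg, Hb 10 to 14 | 20 | 10 | 30/20 = 150% | 40/30 = 133% | 50/40 = 125% |
| <70 kg, Hb 10 to 14 | 20 | 0 | 20/20 = 100% | 30/30 = 100% | 40/40 = 100% |
| Hb >14 to 15 | 10 | 0 | 10/10 = 100% | 20/20 = 100% | 30/30 = 100% |

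All nine values in the first three rows fall in the top category. With Table 7 in the denominator each becomes 100% (30/30, 40/40, 50/50 or 60/60 mL). If ID persists at Week 6, Table 6 expects the same dose and the rate is 100% under either table.

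**Netherlands, Spain and Singapore.** The 10 g/dL limit closes both cells below 10. Only ≥70 kg with Hb 10 to 14 is affected, at 150%, 133% or 125%. This range needs Hb to stay at or above 10 g/dL. Suppose Hb later falls to 8 to <10 with ID present. Table 7 footnote 1 ends further dosing, while Table 6 alone still expects maintenance:
- one such visit, no ID at the other: 30/(20 + 10) = 100%;
- both visits: 30/(20 + 20) = 75%;
- one maintenance dose given, then the fall: 40/(20 + 20) = 100%.

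**Appendix II, protocols 2/3, Visit 3.** The appendix note takes laboratory and vital-sign values closest to the injection, or to the visit if none was given. The last line read that way, with a Week 6 Hb of 14.5:
- 75 kg, screening Hb 12: one line gives 1 kit, another no dose.
- 75 kg, screening Hb 9: 2 kits and no dose.
- 65 kg, screening Hb 9: 1 kit and no dose.
- 65 kg, screening Hb 12: no dose on both lines, so no conflict.

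Only the first conflict can arise in the Netherlands, Spain and Singapore. Conversely, a screening Hb of 14.5 with a Week 6 Hb of 13 matches none of the weight/Hb lines. Weight has the same problem: the lines leave it unqualified, so the note points to the value nearest the injection, whereas Table 7 footnote 2 names the screening value. A subject who crosses 70 kg in between can get a different planned dose under each.

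**The case against.** The best defence is that the section already contains the right rule. Its compliance paragraph cites both tables with a consent and re-consent rule, Appendix II is named as the algorithm, and planned and given totals are summarised in any case. On this view the bullet is a stale cross-reference that a programmer would correct. That is probably how it arose, and nothing suggests that Table 6 was deliberately chosen for protocol 2/3. But this bullet is the only definition of the denominator. The sentence introducing it lists weight, Hb and ID status and omits protocol version and consent date, so nothing beside the formula points to Table 7.

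The objection also limits the figures, and rightly. Two of the five cells are unaffected. The range for the three named countries is conditional: a reader who takes Table 6 alone cannot borrow the 10 g/dL limit from Appendix II while ignoring its version rule.

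On Appendix II, a lost screening qualifier on the last line would explain both the conflicts and the unmatched case. It would not settle which weight is meant, so correcting that line alone would not be enough.

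**Conclusion.** The bullet is wrong as written, and the matter is minor. Under the stated assumptions, the affected subjects score 150/133/125% in two cells and 200/167/150% in a third, with 0, 1 or 2 maintenance doses. In the Netherlands, Spain and Singapore one cell is affected, at 125% to 150%, if Hb stays at or above 10 g/dL; otherwise 75% or 100% is possible. Subjects who change cell between screening and Week 6 are not covered by these figures.

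Three stronger conclusions might be inferred but are not supported:
- **All protocol 2/3 subjects are misreported.** The error needs both absence of ID at Week 6 and one of three cells.
- **Efficacy or the Per-Protocol Set is affected.** Compliance is a Safety Set summary (SAP Table 2), reported in Table 14.1.10.1 and listing 16.2.5.2. No test uses the rate, and the Appendix I dosing exclusions are separate deviation codes that do not refer to it.
- **The error favours one arm.** Protocol 1.2 reports replenished iron stores with ferric carboxymaltose, so absence of ID at Week 6 may be commoner on active treatment. The documents give no counts, and no imbalance can be claimed.

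**What to change.** Before unblinding:

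1. Define the expected amount as the sum over visits of the version-specific planned doses: Table 6 or Table 7 through Appendix II, with the consent and re-consent rule already in 4.8.1. Summing by visit also handles subjects who re-consented during the trial.
2. Reconcile all Appendix II Visit 3 lines for protocols 2/3 with Table 7 and its footnote 2. State which Hb and which weight each line uses, including the last, so that exactly one line applies to each subject. The sponsor decides which passage changes; no dosing rule is proposed here.

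The two changes belong together: after the first, any ambiguity in Appendix II also enters the compliance rate. The cost is one corrected reference, edits to one appendix block and a rerun of the compliance and planned-dose derivations. No new data are needed.

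### The SAP takes the expected dose for the compliance rate from the protocol 1 table alone, so protocol 2 and 3 subjects correctly dosed at Week 6 after iron deficiency has resolved appear over-dosed

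*SAP*

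**What the plan says.** Under Treatment Compliance, SAP 4.8.1 derives each planned dose from the protocol number, the consent and re-consent dates, the pregnancy test, weight, Hb and ID status, using Tables 6 and 7. It states who falls under which table: "Table 7 will apply only for subjects who consented to protocol 2 or 3 or if the subject re-consented to protocol 2", the latter for injections on or after the re-consent date. For protocols 2 and 3, Week 6 dosing is "based on the iron need upon screening Hb and weight values to replete iron as described in Table 7", provided that Week 6 Hb is at most 15 g/dL. Table 6, titled as the protocol 1 regimen, makes the Week 6 dose conditional on ID, for example "2x10 mL (only if ID persists" for the heavier, more anaemic group. Table 7 has no such condition.

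Two results are then produced from these doses:

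- **A per-visit label** (as planned, reduced or increased). "The calculated planned dose and the dose administered as collected in the eCRF will be used to calculate the dosing information", so this result follows the version that applies.
- **A compliance rate**, which is the total volume given divided by the expected volume, times 100, "summarised as continuous and categorical variable (<80, 80-120, > 120 as categories". Its denominator is defined by the line "Expected amount = total volume in mL that should have been administered as described in Table 6". Table 7 is not mentioned there.

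Appendix II holds the planned-dose algorithm, with separate rows for protocols 1.x and for protocols 2 and 3. In the latter, the Visit 3 block ends "Hemoglobin (from screening) in g/dL' ≤ 14 : 1 Kit 'Hemoglobin in g/dL' > 14 : No dose".

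**The concern.** The rate's denominator comes from a regimen under which protocol 2 and 3 subjects were not dosed. Protocol section 12.5 asks for the amount given to be compared with the amount expected for each subject. With Table 6 as the yardstick, a site that followed the current protocol exactly can appear to have over-dosed. The same subject can be labelled as planned at every visit and still fall in the category above 120.

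The error is also unlikely to be balanced between arms. It arises when ID has resolved by Week 6, which intravenous iron should achieve more often than saline. Protocol section 1.2 reports that iron stores were consistently replenished across FCM studies. A compliance table by arm could therefore show apparent over-dosing concentrated in the FCM group.

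**Working it through.** The plan states no compliance figure to reproduce, so the check is to dose subjects exactly per Table 7 and score them against Table 6.

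**Inputs (SAP Tables 6 and 7).**
- Visit 2: 20 mL for Hb 8 to 14, and 10 mL for Hb above 14 to 15, in both tables.
- Week 6 amounts, the same in both tables:
  - under 70 kg: 10 mL for Hb 8 to <10, none for Hb 10 to 14;
  - 70 kg or more: 20 mL for Hb 8 to <10, 10 mL for Hb 10 to 14;
  - Hb above 14: none at any weight.
- Condition for the Week 6 dose: ID persists (Table 6), or screening Hb and weight only (Table 7, with Week 6 Hb at most 15).
- Weeks 12 and 24: 10 mL each if ID is present, in both tables.

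**Main case: protocol 2 or 3, ID absent at Week 6, outside the Netherlands, Spain and Singapore.** Anyone due a Week 6 dose received 20 mL at Visit 2. Let d be the Week 6 dose (10 or 20 mL) and m the number of later visits with ID (0, 1 or 2).

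Given = 20 + d + 10m. Expected by Table 6 = 20 + 0 + 10m. Rate = 100 × given / expected.

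| Group (screening values) | d | m = 0 | m = 1 | m = 2 |
|---|---|---|---|---|
| ≥70 kg, Hb 10–14 | 10 | 30/20 = 150% | 40/30 = 133% | 50/40 = 125% |
| ≥70 kg, Hb 8–<10 | 20 | 40/20 = 200% | 50/30 = 167% | 60/40 = 150% |
| <70 kg, Hb 8–<10 | 10 | 30/20 = 150% | 40/30 = 133% | 50/40 = 125% |
| <70 kg, Hb 10–14; any weight, Hb >14 | 0 | 100% | 100% | 100% |

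Every affected cell is above 120. The result does not depend on whether Table 6 is read with screening or Week 6 Hb, because without ID its Week 6 dose is zero either way. When ID persists and the Hb and weight bands are unchanged, the two tables agree and the rate is 100%.

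**Netherlands, Spain and Singapore.** Table 7 footnote 1 stops dosing once Hb falls below 10 g/dL; Table 6 carries no such footnote. Take a subject of at least 70 kg with screening Hb 11 and no ID at Week 6.
- ID with Hb 9.5 at Weeks 12 and 24. Given 20+10+0+0 = 30. Expected by Table 6 without the limit 20+0+10+10 = 40. Rate 75%, below 80.
- ID at both later visits, Hb 9.5 at Week 24 only. Given 20+10+10+0 = 40, expected 40. Rate 100%, with two errors cancelling.
- First subject with the 10 g/dL limit applied to Table 6: 30 against 20, or 150%.

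**Can Appendix II supply the denominator as it stands?** Not quite. Take at least 70 kg, screening Hb 13.5, Week 6 Hb 14.5. Table 7 footnote 2 gives 10 mL. In Appendix II two Visit 3 lines match: 1 kit (screening Hb at most 14) and no dose (Hb above 14, not marked as from screening). If the last line governs, the planned dose is 0 and the correct 10 mL is labelled increased. With no later ID the rate would again be 30/20 = 150%.

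**The case against.** The strongest reply is that this is a stale cross-reference which a careful programmer would resolve. The planned-dose text cites both tables, so does the exposure paragraph on total planned volume, and Appendix II is split by version. The version-specific planned total is thus already computed. That is fair on the likely cause. It does not remove the conflict, because the line defining the expected amount names Table 6 alone and is the only definition of the denominator.

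Three stronger readings are tempting, and the documents do not support them.

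- **Every protocol 2 or 3 subject without ID at Week 6 is pushed above 120.** The last row of the table stays at 100%, and the three-country examples give 75% and 100%.
- **Correct dosing also shows as gross under-dosing, such as 60%.** In the three countries, a subject of at least 70 kg with screening Hb 11, Week 6 Hb 10.5, ID throughout and Hb 9.5 at Weeks 12 and 24 gives 30 against 50 mL, or 60%. That requires reading Table 6 without Appendix II's country row, which says to "replace lower threshold for Hemoglobin by 10 g/dL instead of 8 g/dL". With that row it is 30 against 30, or 100%. Elsewhere, 60% needs Table 6 read on Week 6 values and an unusual shift, such as Hb falling from above 14 to below 10.
- **Appendix II's country row is wrong for protocols 1.x.** It does differ from 4.8.1, which under 1.2 mentions the 10 g/dL limit for the Netherlands only. The local 1.x protocols are not among the documents, so which text is right cannot be settled, and the number of subjects concerned may be zero.

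**Conclusion.** The point holds. The definition is wrong as written for protocol 2 and 3 subjects who were correctly dosed at Week 6 after ID had resolved. Outside the Netherlands, Spain and Singapore their rate is 125% to 200% and always falls above 120. In those three countries the direction depends on whether the 10 g/dL limit is applied to Table 6. The Appendix II Visit 3 line is a second, smaller conflict with Table 7 footnote 2.

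The figures assume dosing exactly per Table 7 and a literal reading of the denominator. That the FCM arm would be affected more is an expectation from the drug's action. The documents give no proportion with ID resolved at Week 6, so the share of subjects misclassified cannot be stated.

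A reader might infer a threat to the efficacy results. The documents do not support that. The rate feeds only the safety-set exposure and compliance tables and listings (14.1.10.1, 14.1.10.2 and 16.2.5.2 in SAP 7.1). Full analysis set analyses do not use it, and per-protocol exclusion rests on the deviation codes in Appendix I. This is a minor correction, worth making because it is so cheap.

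**What to change.** 1. In SAP 4.8.1, define the expected amount as the sum over visits of the planned dose for the version that applies: Table 6 or Table 7 by consent and re-consent date, with the country Hb limits, as computed in Appendix II. Add what is reported if that sum is zero, as could happen for a subject dosed only outside the Hb limits.
2. In Appendix II, protocols 2 and 3, Visit 3, change the last line so that no dose is planned when Hb from screening is above 14 g/dL. The separate rule of no dose when Hb exceeds 15 stays.

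With both changes, a subject dosed exactly to protocol 2 or 3 scores 100% wherever the expected amount is above zero, and the rate agrees with the per-visit label. The cost is two SAP edits and a few lines of code before unblinding, with no new data.

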		14.1.10.1 Exposure and Compliance - Safety Analysis Set
		14.1.10.2 Exposure and Compliance by Visit - Safety Analysis Set
T	14.2 Efficacy	14.2.1.1.1 Recurrent HF Hospitalisations and CV Death up to 52 Weeks after Randomisation – Full Analysis Set
		14.2.1.1.2 Recurrent HF Hospitalisations and CV Death up to 52 Weeks after Randomisation (Confirmatory Analysis) – Full Analysis Set
		14.2.1.2.1 Recurrent HF Hospitalisations and CV Death up to 52 Weeks after Randomisation – Per Protocol Set
		14.2.1.2.2 Recurrent HF Hospitalisations and CV Death up to 52 Weeks after Randomisation (Confirmatory Analysis) – Per Protocol Set
		14.2.1.3.1 Recurrent HF Hospitalisations and CV Death up to 52 Weeks after Randomisation (Covid-19 Sensitivity Analysis) – Full Analysis Set
		14.2.1.3.2 Recurrent HF Hospitalisations and CV Death up to 52 Weeks after Randomisation (Covid-19 Sensitivity Analysis, Confirmatory Analysis) – Full Analysis Set

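### The compliance denominator in SAP 4.8.1 cites only the protocol 1 dosing table, so protocol 2 and 3 subjects can be misclassified in either direction through the Week 6 dose

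*SAP*

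**What the plan says.** SAP 4.8.1 computes compliance as total volume given divided by expected volume, times 100, and groups it as <80, 80-120 and >120. The denominator is defined in one line: "Expected amount = total volume in mL that should have been administered as described in Table 6". No protocol version is mentioned there.

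Elsewhere the same section uses both tables. The exposure paragraph reads "The total amount of study drug given and planned (see Table 6 and Table 7"). Table 6 is titled for protocol 1 and Table 7 for protocols 2 and 3. Where Table 6 plans a Week 6 dose, it makes it conditional on ID, for example "1x10 mL (only if ID persists"). Table 7 has no such condition at Week 6: "For the protocol 2 and 3, dosing at Week 6 (Visit 3) is based on the iron need upon screening Hb and weight values". Its footnote 2 adds only that Week 6 Hb must not exceed 15 g/dL.

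Table 7 governs anyone whose original consent was to version 2 or version 3. For everyone else it governs only under this condition: "if the subject re-consented to protocol 2 and the injection date is on or after the protocol re-consent date". After the sentence on which laboratory and vital-sign values to use, the section adds: "In case no injection was done, the value closest to the visit date will be used".

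Appendix II gives the planned-dose algorithm separately by protocol version. For protocols 2 and 3, the Visit 3 lines end "Hemoglobin (from screening) in g/dL' ≤ 14 : 1 Kit 'Hemoglobin in g/dL' > 14 : No dose".

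The results feed "14.1.10.1 Exposure and Compliance - Safety Analysis Set" and the companion by-visit table.

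**The concern.** The expected amount for a protocol 2 or 3 subject is tied to a regimen that the subject was not meant to follow. Where the two tables disagree, following the protocol can be reported as over- or under-dosing, and a missed dose can be reported as full compliance.

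The section would also contradict itself. The planned total comes from both tables and the expected total from one, so a subject could have 30 mL planned and 20 mL expected, and be dosed as planned at every visit with a compliance of 150%.

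What is at stake is how the compliance table describes adherence to the dosing scheme.

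**Working it through.** The plan states no compliance figure, so there is none to reproduce. The check applies both tables to the same subjects.

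**Inputs (SAP 4.8.1, Tables 6 and 7, Appendix II)**
- Visit 2, both tables: 20 mL if Hb is 8 to 14 g/dL, 10 mL if above 14 to 15.
- Visits 4 and 5, both tables: 10 mL each if ID persists.
- Week 6 volumes, both tables: below 70 kg, 10 mL for Hb 8 to <10, otherwise none; at 70 kg or more, 20 mL for Hb 8 to <10, 10 mL for Hb 10 to 14, none above 14.
- Week 6 conditions: Table 6 needs persisting ID and, by the protocol 1 rules of Appendix II and the closest-value rule, uses current Hb. Table 7 uses screening Hb, has no ID condition, and requires Week 6 Hb of at most 15.

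**1. ID resolved at Week 6, subject dosed correctly under Table 7.** Let d be the Table 7 Week 6 dose and m the number of maintenance doses given and due. Given volume = 20 + d + 10m. Table 6 expects 20 + 10m. The true rate is 100%.

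| m | d = 10 mL | d = 20 mL |
|---|---|---|
| 0 | 30/20 = 150% | 40/20 = 200% |
| 1 | 40/30 = 133% | 50/30 = 167% |
| 2 | 50/40 = 125% | 60/40 = 150% |

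All six move from 80-120 to >120.

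**2. ID resolved, Week 6 dose missed.** Given volume = 20 + 10m, which equals the Table 6 expectation, so every case scores 100%. Against Table 7:

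| m | d = 10 mL | d = 20 mL |
|---|---|---|
| 0 | 20/30 = 67% | 20/40 = 50% |
| 1 | 30/40 = 75% | 30/50 = 60% |
| 2 | 40/50 = 80% | 40/60 = 67% |

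Five of the six belong in <80 but are reported in 80-120.

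**3. ID persisting.** The error can go either way, or vanish (no maintenance dose given or due):
- 70 kg or more, screening Hb 14.5, Week 6 Hb 13.5: Table 7 plans 10 mL at Visit 2 and none at Week 6, so 10 mL is correct. Table 6 expects 10 + 10 = 20 mL. Score 10/20 = 50% instead of 100%.
- 70 kg or more, Hb rising from 9 to 11: given 40 mL, Table 6 expects 30 mL. Score 133% instead of 100%.
- 70 kg or more, Hb 10 to 14 both times: 30/30 = 100% under both tables.

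**4. Table selection without an injection.** Subjects who first consented to protocol 2 or 3 need no date, and protocol 1 subjects who never re-consented stay on Table 6. The gap concerns only subjects re-consented to protocol 2 with no Week 6 injection. The condition then has no injection date to test and, read strictly, sends them to Table 6. Cross two weight bands, three screening Hb bands, three Week 6 Hb bands (8 to <10, 10 to 14, >14 to 15) and ID yes/no: 36 combinations, with the lower Hb limit at 8 g/dL and the closing Appendix II line read as screening Hb. Table 7 plans a dose in 18, and in 13 of these Table 6 plans none, so a missed dose can be scored as planned. Table 7 plans none in the other 18, and in 4 of these Table 6 plans a dose, so a correct omission can be scored as reduced. These are rule combinations, not subject frequencies. This gap affects by-visit dosing status and total planned volume; it reaches the compliance rate only once the denominator line is corrected.

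**5. Appendix II, protocols 2 and 3, Visit 3.** The four preceding lines specify screening Hb; the closing >14 line does not. Read as Week 6 Hb, it removes the dose in 6 of the 18 combinations where Table 7 plans one (Week 6 Hb >14 to 15). Read as screening Hb, it completes the bands and agrees with footnote 2. Weight is also unqualified, and the closest-value rule would take the Week 6 weight, whereas footnote 2 refers to screening weight.

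**The case against.** The best defence is that the right rule is close by. The denominator line does not say that it covers all subjects. Table 6 is labelled as protocol 1, the compliance paragraphs derive the planned dose from both tables by consent version, and Appendix II gives version-specific rules. A programmer who uses the Appendix II planned dose as the expected amount gets the correct denominator, and the main error disappears. That makes a stale cross-reference the likely explanation and keeps the point small. It does not cure the text: Appendix II is introduced for the planned dose, the expected amount has its own definition, and that definition names Table 6 alone. Two programmers working independently could reasonably differ.

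It is equally fair that the Appendix II >14 line has a clear intended reading and needs only clarification.

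A reader might infer more than the documents support:
- **That compliance is distorted mainly in the FCM arm.** Resolved ID may be commoner on FCM, but the documents give no rates by arm, and errors also arise with persisting ID.
- **That the per-protocol set is affected.** Its dosing exclusions rest on the Appendix I deviation codes (PDIMP01 to PDIMP03), not on this rate.
- **That table selection fails at every visit without an injection.** It fails only for the re-consented subgroup, and the table chosen changes the dose only at Week 6.

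**Conclusion.** The point holds as a minor error of wording with a definite numerical consequence if followed. For protocol 2 and 3 subjects, the literal denominator gives 125% to 200% for correct dosing with resolved ID, 100% for a missed Week 6 dose whose true rate is 50% to 80%, and 50% for a correctly dosed subject in the falling-Hb example.

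The resolved-ID results depend only on the ID condition at Week 6. The falling-Hb example also assumes that Table 6 is applied to current Hb, as Appendix II does for protocol 1. How many subjects are affected cannot be derived from the documents; the re-consented group without a Week 6 injection is probably small.

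The consequence is confined to descriptive Safety Set exposure and compliance outputs. No efficacy analysis uses them.

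**What to change.** **Main change (SAP 4.8.1).** Define the expected amount *as described in Table 6 or Table 7, as applicable (Appendix II)*.

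**Secondary wording.**
1. SAP 4.8.1, table selection: for a subject re-consented to protocol 2 with no Week 6 injection, compare the re-consent date with the visit date.
2. Appendix II, protocols 2 and 3, Visit 3: write *Hemoglobin (from screening) > 14: No dose* and *Weight (from screening/baseline)*, to match Table 7 footnote 2. Keep Week 6 Hb above 15 g/dL as a separate no-dose limit.

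The cost is a few wording edits in 4.8.1 and Appendix II plus the matching derivation code. No new data are needed.
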